11.9 Gender and Minority Accrual Estimates

The gender and minority distribution of the study population is expected to be:

Racial category	Ethnicity				Total	
	Not Hispanic or Latino		Hispanic or Latino			
	Female	Male	Female	Male		
American Indian/Alaska Native	0	0	0	0	0	
Asian	1	1	0	0	2	
Native Hawaiian or Other Pacific Islander	0	0	0	0	0	
Black or African American	3	5	0	0	8	
White	12	20	4	2	38	
More than one race	1	0	0	0	1	
Total	17	26	4	2	49	

This distribution was derived from the demographic data for patients enrolled on recent COG Phase 2 trials.

12.0 EVALUATION CRITERIA

12.1 Common Terminology Criteria for Adverse Events (CTCAE)

The descriptions and grading scales found in the current version of the NCI Common Terminology Criteria for Adverse Events (CTCAE) will be utilized for AE reporting. All appropriate treatment areas should have access to a copy of the current CTCAEv5.0. A copy of the CTCAEv5.0 can be downloaded from the CTEP website (<http://ctep.cancer.gov>).

12.2 Progression-Free Survival

Progression-free survival (PFS) is defined as the duration of time from start of subprotocol treatment to time of progression or death, whichever occurs first.

Development of new disease or progression in any established lesions is considered progressive disease, regardless of response in other lesions – e.g., when multiple lesions show opposite responses, the progressive disease takes precedence.

12.3 Response Criteria for Patients with Solid Tumors

See the table in [Section 8.0](#) for the schedule of tumor evaluations. In addition to the scheduled scans, a confirmatory scan should be obtained on the next consecutive cycle

following initial documentation of objective response.

As outlined, patients will be assigned to one of the following categories for assessment of response: a) solid tumor (non-CNS) and measurable disease ([Section 12.4](#)); b) neuroblastoma with MIBG positive lesions ([Section 12.5](#)); c) CNS tumor ([Section 12.7](#)); and d) Non-Hodgkin lymphoma/histiocytosis ([Section 12.8](#)). Note: Neuroblastoma patients who do not have MIBG positive lesions should be assessed for response as solid tumor patients with measurable disease.

Response and progression will be evaluated in this study using the revised Response Evaluation Criteria in Solid Tumors (RECIST) guideline (version 1.1) [*Eur J Ca* 45:228-247, 2009]. Key points are that 5 target lesions are identified and that changes in the *largest* diameter (unidimensional measurement) of the tumor lesions but the *shortest* diameter of malignant lymph nodes are used in the RECIST v 1.1 criteria.

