Circulating Tumor DNA (ctDNA-optional) ⁹			Cycle 5, Day 1 and (for patients receiving \geq 5 cycles only) at end of Protocol Therapy OR disease progression

[^] Studies may be obtained within 72 hours prior to the start of the subsequent cycle.

- 1 Women of childbearing potential require a negative pregnancy test prior to starting treatment; sexually active patients must use an acceptable method of birth control. Abstinence is an acceptable method of birth control.
- 2 If patients have Grade 4 neutropenia then CBCs should be checked at least every other day until recovery to Grade 3 or until meeting the criteria for dose limiting toxicity.
- 3 If patients develop Grade 3 or higher thrombocytopenia then CBCs should be checked every 3-4 days until recovery per [Section 6.1](#)
- 4 Tumor Disease Evaluation should be obtained on the next consecutive cycle after initial documentation of either a PR or CR. Subsequent scans may restart 2 cycles after the confirmatory scan. If the institutional investigator determines that the patient has progressed based on clinical or laboratory evidence, he/she may opt not to confirm this finding radiographically.

4-A Neurological exam also required for CNS patients

4-B Non- Hodgkin Lymphoma/ Histiocytosis patients are required to have PET scans within 2 weeks prior to start of therapy and should also be followed with PET scans if positive at diagnosis. Refer to [Section 12.8](#)

4-C Patients with neuroblastoma must have both CT/MRI and MIBG scintigraphy prior to enrollment if the patient was enrolled with or has a history of having MIBG avid tumor. Otherwise the patient must have both CT/MRI and bone scan prior to enrollment. For patients with neuroblastoma and measurable disease by CT or MRI, lesions should be measured and followed using the same modality (CT or MRI) in addition to MIBG or bone scan. For patients with neuroblastoma and evaluable disease by MIBG scintigraphy or bone scan, use the same modality (MIBG scintigraphy or bone scan) to image and follow patients; CT/MRI are not required but may be performed as

clinically indicated. Refer to [Section 12.5.4](#) and [Section 12.9](#)

- 5 Bone marrow aspirate and/or biopsy only required in patients suspected of having bone marrow metastasis on the basis of history, symptoms, laboratory evaluation or other clinical data. Should only be performed on patients with known bone marrow involvement at baseline.

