12.4.3 Overall Response Assessment

Table 1: For Patients with Measurable Disease (i.e., Target Disease)

Target Lesions	Non-Target Lesions	New Lesions	Overall Response	Best Overall Response when Confirmation is Required*
CR	CR	No	CR	≥ 28 days Confirmation
CR	Non-CR/Non-PD	No	PR	≥ 28 days Confirmation
CR	Not evaluated	No	PR	
PR	Non-CR/Non-PD/not evaluated	No	PR	
SD	Non-CR/Non-PD/not evaluated	No	SD	documented at least once ≥ 28 days from baseline
PD	Any	Yes or No	PD	no prior SD, PR or CR
Any	PD**	Yes or No	PD	
Any	Any	Yes	PD	

* See RECIST 1.1 manuscript for further details on what is evidence of a new lesion.
 ** In exceptional circumstances, unequivocal progression in non-target lesions may be accepted as disease progression.

Note: Patients with a global deterioration of health status requiring discontinuation of treatment without objective evidence of disease progression at that time should be reported as “*symptomatic deterioration*.” Every effort should be made to document the objective progression even after discontinuation of treatment.

Table 2: For Patients with Non-Measurable Disease (i.e., Non-Target Disease)

Non-Target Lesions	New Lesions	Overall Response
CR	No	CR
Non-CR/non-PD	No	Non-CR/non-PD*
Not all evaluated	No	not evaluated
Unequivocal PD	Yes or No	PD
Any	Yes	PD

* ‘Non-CR/non-PD’ is preferred over ‘stable disease’ for non-target disease since SD is increasingly used as an endpoint for assessment of efficacy in some trials so to assign this category when no lesions can be measured is not advised

Table 3: Overall Response for Patients with Neuroblastoma and Measurable Disease

CT/MRI	MIBG	Bone Scan	Bone Marrow	Catechol	Overall
PD	Any	Any	Any	Any	PD
Any	PD	Any	Any	Any	PD
Any	Any	PD	Any	Any	PD
Any	Any	Any	PD	Any	PD
SD	CR/PR/SD	Non-PD	Non-PD	Any	SD
PR	CR/PR	Non-PD	Non-PD	Any	PR
CR/PR	PR	Non-PD	Non-PD	Any	PR
CR	CR	Non-PD	Non-PD	Elevated	PR
CR	CR	CR	CR	Normal	CR

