12.5 Response Criteria for Neuroblastoma Patients with MIBG Positive Lesions

12.5.1 MIBG Positive Lesions

Patients who have a positive MIBG scan at the start of therapy will be evaluable for MIBG response. The use of ^{123}I for MIBG imaging is recommended for all scans. If the patient has only one MIBG positive lesion and that lesion was radiated, a biopsy must be done at least 28 days after radiation was completed and must show viable neuroblastoma.

12.5.2 The following criteria will be used to report MIBG response by the treating institution:

Complete response: Complete resolution of all MIBG positive lesions

Partial Response: Resolution of at least one MIBG positive lesion, with

persistence of other MIBG positive lesions

Stable disease: No change in MIBG scan in number of positive lesions

Progressive disease: Development of new MIBG positive lesions

[figure not shown]
12.5.3 The response of MIBG lesions will be assessed on central review using the Curie scale¹⁴ as outlined below. Central review responses will be used to assess efficacy for study endpoint. See [Section 8.2](#) for details on transferring images to the Imaging Research Center.

NOTE: This scoring should also be done by the treating institution for end of course response assessments.

The body is divided into 9 anatomic sectors for osteomedullary lesions, with a 10th general sector allocated for any extra-osseous lesion visible on MIBG scan. In each region, the lesions are scored as follows. The **absolute extension score** is graded as:

- 0 = no site per segment,
- 1 = 1 site per segment,
- 2 = more than one site per segment,
- 3 = massive involvement (>50% of the segment).

The **absolute score** is obtained by adding the score of all the segments. See diagram of sectors below:

The **relative score** is calculated by dividing the absolute score at each time point by the corresponding pre-treatment absolute score. The relative score of each patient is calculated at each response assessment compared to baseline and classified as below:

1. **Complete response:** all areas of uptake on MIBG scan completely resolved. If morphological evidence of tumor cells in bone marrow biopsy or aspiration is present at enrollment, no tumor cells can be detected by routine morphology on two subsequent bilateral bone marrow aspirates and biopsies done at least 21 days apart to be considered a **Complete Response**.

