12.5.4 Overall Response Assessment

Table 4: Overall Response Evaluation for Neuroblastoma Patients and MIBG Positive Disease Only

If patients are enrolled without disease measurable by CT/MRI, any new or newly identified lesion by CT/MRI that occurs during therapy would be considered progressive disease.

MIBG	CT/MRI	Bone Scan	Bone Marrow	Catechol	Overall
PD	Any	Any	Any	Any	PD
Any	New Lesion	Any	Any	Any	PD
Any	Any	PD	Any	Any	PD
Any	Any	Any	PD	Any	PD
SD	No New Lesion	Non-PD	Non-PD	Any	SD
PR	No New Lesion	Non-PD	Non-PD	Any	PR
CR	No New Lesion	Non-PD	Non-PD	Elevated	PR
CR	No New Lesion	CR	CR	Normal	CR

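### Section 12.3 has no tie-break for neuroblastoma with both measurable and MIBG-positive disease, and Tables 3 and 4 give different responder status when CT/MRI is stable and MIBG responds

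*Combined protocol and SAP*

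**What the plan says.** Section 12.3 states that "patients will be assigned to one of the following categories for assessment of response". Category a) is non-CNS solid tumor with measurable disease (Section 12.4). Category b) is neuroblastoma with MIBG-positive lesions (Section 12.5), with no exception for patients who also have measurable disease. The Note that follows reads: "Neuroblastoma patients who do not have MIBG positive lesions should be assessed for response as solid tumor patients with measurable disease".

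There are two neuroblastoma overall-response tables:

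- In Section 12.4.3: "Table 3: Overall Response for Patients with Neuroblastoma and Measurable Disease". It combines the CT/MRI response category with MIBG, bone scan, marrow and catecholamines.
- In Section 12.5.4: "Table 4: Overall Response Evaluation for Neuroblastoma Patients and MIBG Positive Disease Only". Its CT/MRI column records only whether a new lesion has appeared. Its lead-in begins: "If patients are enrolled without disease measurable by CT/MRI, any new or newly identified lesion by CT/MRI".

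Footnote 4-C to the Section 8.1 schedule foresees patients with both kinds of disease: "For patients with neuroblastoma and measurable disease by CT or MRI, lesions should be measured and followed using the same modality (CT or MRI"). The footnote asks for a nuclear scan (MIBG or bone) alongside. It then refers the reader to Sections 12.5.4 and 12.9, not to Section 12.4.3.

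On the MIBG component, Section 12.5.3 says: "Central review responses will be used to assess efficacy for study endpoint".

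**The concern.** A patient with both measurable and MIBG-positive disease can be scored by either of two tables. Category b), the Note and footnote 4-C lead to Table 4. Category a) and the table titles lead to Table 3. Table 4 takes no account of whether measured lesions have shrunk, so a patient whose CT/MRI disease is merely stable can become a responder on MIBG alone.

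Responder status is the primary endpoint, and success needs only 3 responders in 20 (Section 11.3.1). The same classification feeds the expansion rule of at least 3 responders in one histology (Section 11.3.2), and neuroblastoma is a listed histology (Appendix VII). Central review does not remove the ambiguity, because Section 12.5.3 settles who scores the MIBG scan and not which overall table applies. If the table were chosen after the scans had been seen, the endpoint would depend on the data.

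**Working it through.** **Step 1: compare the tables.** The rows of Tables 3 and 4 were set against each other for every CT/MRI category, assuming no new CT/MRI lesion and no progression on MIBG, bone scan or marrow. Where MIBG is CR, the overall result is PR if catecholamines are elevated, or CR if bone scan and marrow are also CR and catecholamines are normal.

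| CT/MRI | MIBG | Table 3 | Table 4 | Responder status |
|---|---|---|---|---|
| CR | CR | PR or CR | PR or CR | same |
| CR | PR | PR | PR | same |
| PR | CR | PR | PR or CR | same (responder) |
| PR | PR | PR | PR | same |
| CR or PR | SD | no row | SD | undefined in Table 3 |
| SD | PR | SD | PR | **changes** |
| SD | CR | SD | PR or CR | **changes** |
| SD | SD | SD | SD | same |
| PD by growth | CR, PR or SD | PD | follows MIBG | settled by Section 12.2: PD |

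Two combinations therefore change responder status with nothing elsewhere in the protocol to settle them: CT/MRI SD with MIBG PR, and CT/MRI SD with MIBG CR. Two more, CT/MRI CR or PR with MIBG SD, have no Table 3 result.

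**Step 2: reproduce the plan's design.** Inputs from Section 11.3.1: N = 20, success at 3 or more responses, 5% against 25%, alpha 10%, power 90%.

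- Alpha = 1 − P(0) − P(1) − P(2) at 5% = 1 − 0.3585 − 0.3774 − 0.1887 = 0.0755.
- Power = the same expression at 25% = 1 − 0.0032 − 0.0211 − 0.0669 = 0.9087 (from unrounded terms).

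The exact alpha lies under the 10% ceiling, the power agrees with 90%, and N = 20 is the smallest single-stage design meeting both. The design is sound; the question is what is counted as a response.

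**Step 3: leverage of one patient.** Suppose one of the 20 has CT/MRI SD with MIBG PR or CR. Table 3 counts 0 for that patient and Table 4 counts 1. The decision differs only if the other 19 have exactly 2 responders, with probability C(19,2) p² (1 − p)¹⁷, where C(19,2) = 171:

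- p = 5%: 171 × 0.0025 × 0.95¹⁷ = 0.179
- p = 10%: 171 × 0.01 × 0.90¹⁷ = 0.285
- p = 25%: 171 × 0.0625 × 0.75¹⁷ = 0.080

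These probabilities are conditional on such a patient being present. The documents give no expected number of patients with both disease types and no rate of discordant CT/MRI and MIBG response, so an unconditional figure cannot be derived.

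**The case against.** The best defence is that the protocol already shows which table is meant. Table 3 is titled for neuroblastoma with measurable disease and has an MIBG column. Table 4 is titled for MIBG-positive disease only, and its lead-in concerns patients without CT/MRI-measurable disease. Eligibility criterion 4.1.4 and footnote 4-C draw the same line between measurable and evaluable disease. On this view, scoring such a patient as PR means using a table whose title excludes the patient. That argument stands as evidence of intent, and it determines the fix. It does not remove the conflict, because category b), the Note and footnote 4-C still point the other way.

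Three stronger readings are tempting, and the documents do not support them.

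- A reader might infer that Section 12.3 sends every MIBG-positive patient to Table 4. A neuroblastoma patient with measurable disease also literally fits category a), and the Note does not bar MIBG-positive patients from Section 12.4. The defect is an overlap without a tie-break.
- A reader might infer that growth of a CT lesion with an MIBG response would count as PR. Section 12.2 makes progression in any established lesion PD whatever other lesions do, and Section 10.1 removes patients with radiographic progression from therapy.
- A reader might infer an inflated type I error. That needs an assumed number of such patients and an assumed chance of discordant response, and the documents give neither. The number could be zero.

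**Conclusion.** The concern holds as an unresolved overlap in Section 12.3. For neuroblastoma with both disease types, CT/MRI SD with MIBG PR or CR is a non-response by Table 3 and a response by Table 4, and the protocol's pointers disagree on which to use. One such patient would change the primary decision with probability 18%, 29% or 8% at true response rates of 5%, 10% or 25% in the other 19. This assumes independent patients with a common response rate, and an MIBG response that is repeated as Section 12.9 requires and upheld on central review. How often it would arise is unknown. The titles make Table 3 the likely intent, so this is a wording correction with a possible effect on the primary endpoint and not a fault in the design.

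**What to change.** - In Section 12.3, state that neuroblastoma with measurable disease, with or without MIBG-positive lesions, is assessed by Table 3, and that MIBG-positive disease without measurable disease is assessed by Table 4.
- For patients without MIBG-positive lesions, mark the MIBG column of Table 3 as not applicable and keep the bone scan, marrow and catecholamine columns. As printed, every SD, PR and CR row needs an MIBG category that these patients lack. Sending them to Table 1 instead would drop the other three columns, although Section 12.6.1 treats marrow as part of overall response.
- Add Section 12.4.3 to the cross-reference in footnote 4-C.
- Add the missing Table 3 rows for CT/MRI CR or PR with MIBG SD. These decide responder status, so they must be fixed before any response is adjudicated.

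The cost is protocol wording only. No extra scans are needed, because footnote 4-C already has these patients followed by both kinds of imaging. The downside is that a patient with an MIBG response but stable CT/MRI disease is not counted as a responder.

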12.3.1 Definitions

12.3.1.1 Evaluable for objective response:

Eligible patients who receive at least one dose of protocol therapy will be considered evaluable for response. Evaluable patients who demonstrate a complete or partial response confirmed by central review before receiving non-protocol anti-cancer therapy will be considered a responder. All other evaluable patients will be considered non-responders

12.3.1.2 Evaluable Non-Target Disease Response:

Eligible patients who have lesions present at baseline that are evaluable but do not meet the definitions of measurable disease and have received at least one dose of protocol therapy will be considered evaluable for non-target disease response. The response assessment is based on the presence, absence, or unequivocal progression of the lesions.

12.3.2 Disease Parameters

12.3.2.1 Measurable disease: Measurable lesions are defined as those that can be accurately measured in at least one dimension (longest diameter to be recorded) as ≥ 20 mm by chest x-ray, as ≥ 10 mm with CT scan, or ≥ 10 mm with calipers by clinical exam. All tumor measurements must be recorded in millimeters (or decimal fractions of centimeters).

Note: Tumor lesions that are situated in a previously irradiated area might or might not be considered measurable. If the investigator thinks it appropriate to include them, the conditions under which such lesions should be considered must be defined in the protocol.

12.3.2.2 Malignant lymph nodes: To be considered pathologically enlarged and measurable, a lymph node must be ≥ 15 mm in short axis when assessed by CT scan (CT scan slice thickness no greater than 5 mm). At baseline and in follow-up, only the short axis will be measured and followed.

12.3.2.3 **Non-measurable disease:** All other lesions (or sites of disease), including small lesions (longest diameter < 10 mm or pathological lymph nodes with ≥ 10 to < 15 mm short axis), are considered non-measurable disease. Bone lesions, leptomeningeal disease, ascites, pleural/pericardial effusions, lymphangitis cutis/pulmonitis, inflammatory breast disease, and abdominal masses (not followed by CT or MRI), are considered as non-measurable.

Note: Cystic lesions that meet the criteria for radiographically defined simple cysts should not be considered as malignant lesions (neither measurable nor non-measurable) since they are, by definition, simple cysts. 'Cystic lesions' thought to represent cystic metastases can be considered as measurable lesions, if they meet the definition of measurability described above. However, if non-cystic lesions are present in the same patient, these are preferred for selection as target lesions.

12.3.2.4 **Target lesions:** All measurable lesions up to a maximum of 2 lesions per organ and 5 lesions in total, representative of all involved organs, should be identified as target lesions and recorded and measured at baseline. Target lesions should be selected on the basis of their size (lesions with the longest diameter), be representative of all involved organs, but in addition should be those that lend themselves to reproducible repeated measurements. It may be the case that, on occasion, the largest lesion does not lend itself to reproducible measurement in which circumstance the next largest lesion that can be measured reproducibly should be selected. A sum of the diameters (longest for non-nodal lesions, short axis for nodal lesions) for all target lesions will be calculated and reported as the baseline sum diameters. If lymph nodes are to be included in the sum, then only the short axis is added into the sum. The baseline sum diameters will be used as reference to further characterize any objective tumor regression in the measurable dimension of the disease.

12.3.2.5 **Non-target lesions:** All other lesions (or sites of disease) including any measurable lesions over and above the 5 target lesions should be identified as non-target lesions and should also be recorded at baseline. Measurements of these lesions are not required, but the presence, absence, or in rare cases unequivocal progression of each should be noted throughout follow-up.

12.3.3 **Methods for Evaluation of Measurable Disease**

All measurements should be taken and recorded in metric notation using a ruler or calipers.

The same method of assessment and the same technique should be used to characterize each identified and reported lesion at baseline and during follow-up. Imaging-based evaluation is preferred to evaluation by clinical examination unless the lesion(s) being followed cannot be imaged but are assessable by clinical exam.

12.3.3.1 **Clinical lesions:** Clinical lesions will only be considered measurable when they are superficial (e.g., skin nodules and palpable lymph nodes) and ≥ 10 mm diameter as assessed using calipers (e.g., skin nodules). In the case of skin lesions, documentation by color photography, including a ruler to estimate the size of the lesion, is recommended.

12.3.3.2 **Chest x-ray:** Lesions on chest x-ray are acceptable as measurable lesions when they are clearly defined and surrounded by aerated lung. However, CT is preferable.

12.3.3.3 **Conventional CT and MRI:** This guideline has defined measurability of lesions on CT scan based on the assumption that CT slice thickness is 5 mm or less. If CT scans have slice thickness greater than 5 mm, the minimum size for a measurable lesion should be twice the slice thickness. MRI is also acceptable in certain situations (e.g. for body scans). Ideally, the same type of scanner should be used and the image acquisition protocol should be followed as closely as possible to prior scans.

12.3.3.4 **PET-CT:** At present, the low dose or attenuation correction CT portion of a combined PET-CT is not always of optimal diagnostic CT quality for use with RECIST measurements. However, if the site can document that the CT performed as part of a PET-CT is of identical diagnostic quality to a diagnostic CT (with IV and oral contrast), then the CT portion of the PET-CT can be used for RECIST measurements and can be used interchangeably with conventional CT in accurately measuring cancer lesions over time. Note, however, that the PET portion of the CT introduces additional data which may bias an investigator if it is not routinely or serially performed.

12.3.3.5 **Tumor markers:** Tumor markers alone cannot be used to assess response. If markers are initially above the upper normal limit, they must normalize for a patient to be considered in complete clinical response.

12.3.3.6 **Cytology, Histology:** These techniques can be used to differentiate between partial responses (PR) and complete responses (CR) in rare cases (e.g., residual lesions in tumor types, such as germ cell tumors, where known residual benign tumors can remain).

Cytology should be obtained if an effusion appears or worsens during treatment when the measurable tumor has met criteria for response or stable disease.

12.3.3.7 **FDG-PET:** While FDG-PET response assessments need additional study, it is sometimes reasonable to incorporate the use of FDG-PET scanning to complement CT scanning in assessment of progression (particularly possible 'new' disease). New lesions on the basis of FDG-PET imaging can be identified according to the following algorithm:

- Negative FDG-PET at baseline, with a positive FDG-PET at follow-up is a sign of PD based on a new lesion.

b. No FDG-PET at baseline and a positive FDG-PET at follow-up: If the positive FDG-PET at follow-up corresponds to a new site of disease confirmed by CT, this is PD. If the positive FDG-PET at follow-up is not confirmed as a new site of disease on CT, additional follow-up CT scans are needed to determine if there is truly progression occurring at that site (if so, the date of PD will be the date of the initial abnormal FDG-PET scan). If the positive FDG-PET at follow-up corresponds to a pre-existing site of disease on CT that is not progressing on the basis of the anatomic images, this is not PD.

Note: A 'positive' FDG-PET scan lesion means one that is FDG avid with an uptake greater than twice that of the surrounding tissue on the attenuation corrected image.

For patients with a positive PET scan at diagnosis, PET can be used to follow response in addition to a CT scan using the International Pediatric non-Hodgkin Lymphoma Response Criteria.³¹

Response Criteria for Patients with Solid Tumor and Measurable Disease

